10.2.4 Time to response

TTR will be derived for all subjects achieving PR or CR. TTR will be summarized using descriptive statistics.

10.2.5 Overall survival

OS will be summarized, analysed, and presented graphically as described for DOR. If a subject is not known to have died, then OS will be censored, and the censoring date will be the latest date the subject was known to be alive (on or before the cut-off date).

OS, using the FAS, will also be summarized and graphed separately for overall MRD negativity status as described in Section 5.2.4.

Survival status, as assessed at regularly scheduled intervals after the completion of treatment, will be listed chronologically by subject.

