5.2.4 Minimal residual disease (MRD) determination

The level of minimum residual disease (MRD) will be assessed based on results from B-cell receptor (BCR) sequencing at timing of the radiological assessments. The level of MRD may conceptually be classified as “negative” (if MRD level is below a cut-off) or “positive” (if MRD level is above a cut-off). Three cut-offs may be used to classify the level of MRD: 10^{-4} , 10^{-5} , and 10^{-6} , where 10^{-5} is considered as the primary cut-off, and the others may be used for sensitivity analysis.

Given a cut-off, the “overall MRD status” is defined as:

- “MRD negative (cut-off)” as having at least one MRD negative result while on treatment (may or may not have indeterminate result)
- “MRD positive (cut-off)” as lacking an MRD negative result while on treatment (subjects who are continuously MRD positive, MRD indeterminant, not tested, or missing MRD samples throughout trial)

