Overall survival (OS) will be calculated in days as:

OS = date of death from any cause – date of first dose of investigational treatment + 1

Subjects not known to have died will be censored at the last date known to be alive.

Time to next anti-lymphoma treatment (TTNT) will be calculated in days as:

TTNT = date of first recorded administration of subsequent anti-lymphoma therapy – date of first dose of investigational treatment + 1

In the absence of recorded subsequent anti-lymphoma therapy, subjects will be censored at the last non-missing disease assessment.

Time to response (TTR) will be calculated in days as:

TTR = date of first response – date of first dose of GEN3009 + 1

TTR will only be calculated for those subjects achieving CR or PR.

Sustained MRD negative response will be calculated as described in Section 10.2.8.

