10.2.3 Progression-free survival

PFS will be summarized, analysed, and presented graphically as described for DOR. Subjects without a documented progression or death will be censored following the rule laid out in Section 5.3.1.

If feasible, PFS analysis may be also stratified by overall MRD status (negative or positive as per definition in Section 10.2.7)

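### OS from first dose is graphed by ever-MRD-negative status, with untested subjects counted as positive, so the curves favour the negative group even if MRD has no effect

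*SAP*

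**What the plan says.** SAP 10.2.5 commits to the OS display: "OS, using the FAS, will also be summarized and graphed separately for overall MRD negativity status". SAP 10.2.3 makes the PFS version optional, if feasible: "PFS analysis may be also stratified by overall MRD status".

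SAP 5.2.4 defines the groups. Negative means "having at least one MRD negative result while on treatment (may or may not have indeterminate result"). Positive means lacking such a result, and the SAP spells out who is included: "subjects who are continuously MRD positive, MRD indeterminant, not tested, or missing MRD samples throughout trial".

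SAP 5.4 sets the OS clock as "OS = date of death from any cause – date of first dose of investigational treatment + 1", and PFS also runs from Day 1 of Cycle 1. SAP 5.8 ends the on-treatment period 28 days after the last dose.

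Protocol Table 9 schedules MRD blood samples on Day 1 of Cycles 1, 2, 3, 5, 7 and 10, then from Cycle 13 at six-month intervals, with an extra sample when CR is reached. Neither document gives a landmark time, a time-dependent MRD covariate or a separate untested category for the survival displays.

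**The concern.** Group membership is decided after time zero, by an event that can occur only in subjects still alive and on treatment. The first post-dose sample is at C2D1 (Day 29). Anyone who dies or stops before then is positive by rule, and each further cycle survived brings another chance to become negative. The extra sample at CR gives responders one more chance, and the on-treatment restriction ties the label to treatment duration.

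The SAP's exploratory objectives include evaluating the potential surrogacy of biomarkers with PFS and OS, and the protocol names MRD status for that purpose. These curves are what a reader would look at for it. As planned, they cannot separate a real MRD association from the requirement to have lived long enough to be sampled.

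**Working it through.** The documents give no survival rate, MRD rate or event count for this comparison, so there is no planned figure to reproduce. The direction follows from the definitions; the size needs assumptions.

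**Assumptions (not in the documents).** Median PFS 16–26 weeks; median OS 40–60 weeks, with OS equal to PFS plus post-progression survival; sampling until progression at Weeks 4, 8, 16, 24, 36 and 48 (the Day 1 visits of Cycles 2, 3, 5, 7, 10 and 13); a chance q of 15–25% that each sample is negative, unrelated to prognosis; cut-off at 104 weeks.

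**Step 1: how the label tracks survival.** With exponential PFS of median m weeks, the share with no post-dose sample is 1 − 2^(−4/m): 15.9% for m = 16 and 10.1% for m = 26. All of these are called positive. After k samples the chance of being called negative is 1 − (1 − q)^k. That is 0 for k = 0, 15–25% for k = 1, and 1 − 0.85^6 = 62% to 1 − 0.75^6 = 82% for k = 6. The label depends on time under observation even though MRD carries no information.

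**Step 2: null simulation.** The OS event-rate ratio, negative to positive, is about 0.6 to 0.7; for example, medians of about 59 and 38 weeks. A nominal 5% log-rank on OS rejects in about 12–22% of null cohorts of 20, and 29–46% if three cohorts are pooled to 60.

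**Step 3: other assumptions.** A second null simulation varied median OS from 4 to 24 months, with q of 10% or 30% and a 24-month cut-off:

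| Model | OS hazard ratio | OS rejection, n=20 | OS rejection, n=60 |
|---|---|---|---|
| Sampled while alive | 0.25–0.52 | 17–70% | 45–99% |
| Sampled until progression (median PFS 2–6 months) | 0.59–0.76 | 6–14% | 7–28% |

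In the second model the PFS hazard ratio was 0.31–0.51. The rejection rate moves a great deal with the assumptions, but the hazard ratio favoured negative in every scenario.

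**Step 4: the same data with a landmark.** The landmark was C3D1 (Day 57), with the clock starting there, only progression-free, on-treatment subjects included, and status fixed from the C2D1 and C3D1 samples. The null OS hazard ratio becomes 0.99–1.01. Nominal rejection is 5.1–7.0% at n=60 and 4.7–10.6% at n=20, where the large-sample test is itself approximate. If the landmark instead keeps everyone alive and still calls unsampled subjects positive, the second model leaves a hazard ratio of 0.87–0.90. The landmark alone is therefore not enough.

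**Step 5: subjects left from a cohort of 20.** Using 20 × 2^(−t/m) for m = 16 and m = 26:
- Week 8 (C3D1): 14.1 and 16.2
- Week 12: 11.9 and 14.5
- Week 16 (C5D1): 10.0 and 13.1

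At Week 12, with two samples taken, the expected number negative runs from 11.9 × (1 − 0.85²) = 3.3 to 14.5 × (1 − 0.75²) = 6.3.

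**The case against.** The output is exploratory and descriptive. SAP 3.4 rules out formal hypothesis testing, and protocol 11.4.2 treats any P value as hypothesis-generating. No primary endpoint, dose decision or stopping rule depends on it. Protocol 9.8.1 allows biomarker analyses to be deferred or dropped, and SAP Section 12 sends BCR clonality results to a separate report.

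These points limit the consequence but do not remove the artefact: a Kaplan-Meier plot built on this split misleads whether or not a P value is attached, and 10.2.5 still commits to it.

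A reader might go further and infer one of the following, which the documents do not support:
- **The trial's false-positive rate is inflated.** No log-rank by MRD status is planned, so the rejection rates above only gauge the size of the artefact.
- **The pooled or PFS figures describe the planned output.** SAP Section 10 analyses each diagnosis cohort independently, with at most 20 subjects each. SAP 5.1 permits overall summaries where appropriate, but pooling is not the default, and the PFS split is optional.
- **Every cohort will look prognostic.** At n=20, most null cohorts would show no nominal OS difference. The shift is in expectation.
- **Counting untested subjects as positive is wrong throughout.** For the MRD-negativity proportion on the FAS (SAP 10.2.7) it is a conservative rule. The fault lies in reusing it to split survival curves.

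**Conclusion.** The concern holds for the planned OS display and, if it is produced, the PFS display. The bias is built into the definitions, and its direction does not depend on the assumptions. Its size does: an OS event-rate ratio of about 0.6 to 0.7 rests on assumed PFS, OS and per-sample negativity rates, and wider assumptions gave hazard ratios from 0.25 to 0.76. The harm is confined to interpretation of the exploratory MRD-surrogacy objective. The SAP should be changed, but the primary efficacy and safety conclusions are unaffected.

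**What to change.** For the survival displays in SAP 10.2.5 and 10.2.3 only:

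- Replace the split with a landmark analysis at a scheduled MRD blood visit, for example C3D1 or C5D1. Week 12 is an imaging visit, not a scheduled MRD visit.
- Start the clock at the landmark. Include subjects alive and progression-free with at least one evaluable post-dose MRD result by then. Fix status from samples up to that visit.
- Exclude the C1D1 predose sample explicitly. SAP 5.8 starts the on-treatment period on the date of first dose, so that sample could otherwise count.
- Report untested and indeterminate subjects separately in these displays.
- Alternatively, model MRD as a time-dependent covariate.

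Leave the 5.2.4 rule unchanged for the FAS MRD-negativity proportion.

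The cost is SAP wording and reprogramming of exploratory outputs. It fits the update the SAP needs anyway, since it is written to protocol version 4.0 and the protocol is now at version 7.0. The statistical cost is fewer subjects (about 12–15 of 20 at Week 12 under the assumptions, somewhat more at C3D1 and fewer at C5D1), and subjects who turn negative later count as not negative at the landmark.

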10.2.6 Time to next anti-lymphoma therapy

TTNT will be derived for all subjects receiving trial treatment. The number of subjects treated, as well as the numbers subsequently undergoing a non-trial anti-lymphoma therapy and those censored without undergoing another anti-lymphoma therapy, will be presented by cohort.

TTNT will be summarized, analysed, and presented graphically as described for DOR.

10.2.7 Proportion of MRD negative subjects

The proportion of MRD negative subjects, as defined in Section 5.2.4, will be summarized by cycle (with the proportion being dependent on number of subjects starting each cycle) and across trial duration, for each cohort. Summarizes will be presented as described for the primary efficacy endpoint, using the FAS.

Similar summaries will be presented for the subgroup of complete responders.

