		Screening	1d	2d	2d+2h	4d	8d	15d	16d	22d
Day										
Visit window										
Tumor biopsy	9.7/9.8.2	X ^a						X ^{b,f}		
Cytokines	9.8.3.2		X ^c					X ^c		
Complement	9.8.3.3		X ^c	X ^{d,h}	X ^{d,i}			X ^c	X ^d	
Immunophenotyping	9.8.3.1		X ^c	X ^{d,h}		X ^{d,i}		X ^c	X ^d	
PBMC	9.8.3.1		X ^c				X ^{c,d}	X ^{c,d}		X ^{c,d}
Saliva DNA	9.8.3.4	X								
ctDNA/MRD plasma	9.8.3.4/9.2.2.3		X ^c					X ^{c,f}		

Treatment Cycle: 28-day cycle	Section	Cycle 3		Cycle 4-9		Cycle 10 and Beyond		Unscheduled	Treatment Discontinuation Visit
		1d	15d	1d	15d	1d			
Day			+2d	+3d	±3d	±4d			
Visit window									
Tumor biopsy	9.7/9.8.2								X ^b
Cytokine	9.8.3.2							X	
Complement	9.8.3.3			X ^e	X ^e	X ^e		X	X
Immunophenotyping	9.8.3.1	X ^c	X ^c	X ^{c,e}	X ^{c,e}	X ^{c,e}		X	
PBMC	9.8.3.1			X ^{c,e}				X	X
Saliva DNA	9.8.3.4								
ctDNA/MRD plasma	9.8.3.4/9.2.2.3	X ^c		X ^{c,g}		X ^{c,g}		X	

a. Fresh lymph node biopsy (to be taken from patients with easily accessible lesions) or an archival lymph node biopsy (formalin-fixed paraffin-embedded [FFPE], which is taken after most recent therapy prior to enrollment and taken within 6 months of Cycle 1 Day 1) is mandatory for lymphoma, SLL and CLL. Baseline biopsy samples are requested to be submitted by C1D1.

- b. Unless otherwise agreed with sponsor's medical monitor or delegate, a fresh core biopsy is to be taken from patients with easily accessible lesions in Cycle 2 (Week 6) and at the End of Treatment visit.
- c. If the visit occurs on an infusion day, the sample must be taken before IMP treatment (-30 minutes).
- d. Cycle 1 only.
- e. Samples in even cycles only, starting Cycle 4.
- f. Cycle 2 only.
- g. Samples to be taken C5, C7, C10 and C13 only. After C13 a sample will be obtained every 6 months (± 1 month) for up to 3 years.
- h. Only in case of full infusion on Day 1
- i. Only in case of split dose between Day 1 and Day 2

Table 9 Visit Assessment Schedule for MRD – Dose Escalation and Expansion GEN3009 Monotherapy

	Cycles 1, 2, 3, 5, 7, and 10	Cycle 13 and onward
Day or Time post dose (window)	Day 1 (+2 days)	Day 1 (+2 days)
Whole blood MRD ^a	X	A whole blood sample will be obtained every 6 months (\pm 1 month) for up to 3 years

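### The by-cycle MRD-negative rate in SAP 10.2.7 can rise through drop-out alone, and half of Cycles 1 to 12 have no scheduled blood sample behind it

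*SAP*

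**What the plan says.** SAP 10.2.7 plans two summaries of MRD negativity in one sentence. The first "will be summarized by cycle (with the proportion being dependent on number of subjects starting each cycle". The second runs "and across trial duration, for each cohort". The next sentence adds: "Summarizes will be presented as described for the primary efficacy endpoint, using the FAS". For status, 10.2.7 refers back to SAP 5.2.4, which defines only an overall status. A subject is MRD negative "as having at least one MRD negative result while on treatment". The overall MRD-positive group is everyone else: "subjects who are continuously MRD positive, MRD indeterminant, not tested, or missing MRD samples throughout trial". SAP 5.2.4 also places MRD testing "at timing of the radiological assessments".

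In the current protocol, Table 9 (escalation and monotherapy expansion) schedules whole-blood MRD on Day 1 of "Cycles 1, 2, 3, 5, 7, and 10", and from Cycle 13 "A whole blood sample will be obtained every 6 months", for up to 3 years. Table 14 gives the same cycles for the combination cohort. A footnote to both tables adds a blood sample when CR is reached on PET-CT, unless another collection falls within 2 weeks. Marrow aspirate taken to confirm CR is also tested, and Table 8 allows unscheduled samples.

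Protocol Section 4.1 continues monotherapy until progression, unacceptable toxicity, death or end of trial.

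**The concern.** The subjects starting a given cycle are those who have not yet progressed or left for another reason. If MRD-positive subjects progress sooner, they leave the denominator sooner, and the proportion among the rest goes up although no one has converted. With 20 subjects per monotherapy cohort, a few departures move the percentage a long way. A reader who sees higher percentages in later cycles could take them for deepening remission.

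The second difficulty is that the table runs by cycle while blood is drawn only in some cycles. Subjects who start an unsampled cycle enter the denominator with no scheduled result, and 10.2.7 does not say how they count.

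The SAP treats these matters differently elsewhere. Its general rule in Section 5.1 uses the number with an assessment at the visit where that number is displayed, and otherwise the column total. SAP 10.2.8, on sustained MRD negativity, uses the FAS as a fixed denominator. The by-cycle rule follows neither.

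**Working it through.** The plan states no MRD rate, so there is no figure to reproduce. The inputs from the documents are the denominator rule (SAP 10.2.7), the draw schedule (Protocol Tables 9 and 14), the imaging schedule (Protocol 9.2.2.1) and the cohort size of 20 (Protocol 4.1). The starting MRD rate and the drop-out rates are assumptions.

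**1. Effect of the denominator.** Let 30% be negative at the start and let nobody change status. Let a fraction *dn* of negatives and *dp* of positives leave per cycle. Then at Cycle *c*:

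rate(c) = 0.3(1−dn)^(c−1) / [0.3(1−dn)^(c−1) + 0.7(1−dp)^(c−1)]

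The numerator alone is the proportion of everyone who started treatment.

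| Cycle | dn 3%, dp 15%: cycle starters | same case: all treated | dn 5%, dp 10%: cycle starters |
|---|---|---|---|
| 3 | 0.282/(0.282+0.506) = 36% | 28% | 0.271/(0.271+0.567) = 32% |
| 7 | 0.250/(0.250+0.264) = 49% | 25% | 0.221/(0.221+0.372) = 37% |
| 13 | 0.208/(0.208+0.100) = 68% | 21% | 0.162/(0.162+0.198) = 45% |

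If dn = dp, the loss terms cancel and the rate stays at 30%. If negatives leave faster, it falls.

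**2. The same effect in counts.** Assume a cohort of 20 in which 20, 16, 12, 10 and 8 subjects start Cycles 2, 3, 5, 7 and 10, and the same 4 are negative and stay. The by-cycle rate is 4/20, 4/16, 4/12, 4/10 and 4/8, which is 20.0%, 25.0%, 33.3%, 40.0% and 50.0% (Clopper-Pearson 95% CI at Cycle 10: 15.7 to 84.3). On the FAS it is 4/20 = 20.0% throughout (5.7 to 43.7). With 2 negatives the by-cycle rate goes from 10% to 25%, and with 6 from 30% to 75%.

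**3. Cycles with no scheduled draw.** Cycles 1 to 12 without {1, 2, 3, 5, 7, 10} leave {4, 6, 8, 9, 11, 12}. After Cycle 13, six months is about 6.5 cycles, so draws fall near Cycles 19–20, 26 and 32–33, and most later cycles have none.

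**4. What can still fall in those cycles.** With no dose delays, Day 1 of Cycles 2, 3, 5, 7, 10 and 13 is at Weeks 4, 8, 16, 24, 36 and 48. A first CR at the Week 12 scan (Weeks 11 to 13) is 3 to 4 weeks from the nearest draws, so the extra sample is due; at Weeks 12 and 13 it lies in calendar Cycle 4. Scans at Weeks 24, 36 and 48 (±2 weeks) are within 2 weeks of the Cycle 7, 10 and 13 draws and trigger nothing extra on that calendar.

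**5. Value shown in an unsampled cycle.** Take Cycle 6 in the 3%/15% case. If status must come from that cycle, and only scheduled blood draws exist, the figure is 0%. If ever-negative status is carried forward, it is 0.258/(0.258+0.311) = 45%. The SAP does not choose between them.

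**6. Timing.** SAP 5.2.4 ties MRD to imaging, which the protocol labels Cycles 2, 3, 5, 6, 9 and 12. Tables 9 and 14 use Cycles 1, 2, 3, 5, 7 and 10. In a table organised by cycle, the two give different rows.

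**The case against.** The strongest reply is that the by-cycle table is not the MRD result. The across-trial FAS summary has no shrinking denominator, and it agrees with Protocol 11.8.6, which counts subjects with at least one negative sample. The trial tests no formal hypotheses, and the protocol makes MRD exploratory in escalation and the monotherapy cohorts. That stands and limits the weight of the point. It does not repair the by-cycle table, and SAP Section 10 lists the MRD rate as a secondary efficacy endpoint.

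Three stronger readings are tempting, and the documents do not support them:

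- A reader might infer that the six cycles will hold no MRD data. CR-triggered, marrow and unscheduled samples can fall there. They would come mainly from complete responders, so they are selective, but they are data.
- A reader might infer that untested subjects count as positive in each unsampled cycle. That wording in SAP 5.2.4 defines an overall status across the trial. A subject negative in Cycle 3 is not made positive because Cycle 4 had no draw.
- A reader might infer that the rate must climb. It climbs only if positives leave faster. This is plausible because progression ends treatment, but the drop-out rates above are assumed.

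It is also fair to object that an FAS denominator creates its own artefact. In the 3%/15% case it falls to 28%, 25% and 21% although nobody changes status. The FAS rate should therefore stand beside the on-treatment rate and not replace it.

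Finally, the SAP was written against protocol v4.0, whose MRD schedule is not among the documents. The mismatch shown is with the current protocol.

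**Conclusion.** The concern holds in a limited form. The by-cycle denominator in SAP 10.2.7 depends on who is still on treatment, and the rate can rise with no new negatives. The size depends on assumed losses: by Cycle 13, a constant 30% would show as 45% to 68% in the two cases with faster loss of positives, and as 30% with equal losses. Half of Cycles 1 to 12 and most cycles after 13 have no scheduled blood draw. The figure there would be near zero or a carried-forward status, depending on a choice that the SAP leaves open.

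It would go too far to conclude that the MRD analysis as a whole is biased. The across-trial FAS rate does not share the problem, and the SAP plans no trend test or curve of MRD over cycles. The risk lies in how a table of rising percentages would be read.

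**What to change.** Change SAP 10.2.7 as follows:

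- Limit the by-cycle table to the scheduled MRD time points: Cycles 2, 3, 5, 7, 10 and 13, then 6-monthly, with Cycle 1 Day 1 as baseline.
- At each time point, show the number starting the cycle, the number sampled and the number MRD-negative on that sample.
- Give the proportion of the FAS, counting off-treatment or unsampled subjects as not shown to be negative, beside the on-treatment rate. Label both, and state that neither is to be read as a trend in depth of remission.
- State that by-cycle status is cycle-specific.
- Name the across-trial FAS rate as the main MRD result.

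In SAP 5.2.4, reconcile the imaging-based MRD timing with Protocol Tables 9 and 14.

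The cost is SAP wording and a few table columns, with no new data. Later-cycle figures on the FAS denominator will be lower and conservative.

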10.2.8 Sustained MRD negative response

Once CR is reached, the MRD level will be assessed on a 6-monthly interval. The proportion of subjects (out of the number subjects included in FAS) with sustained MRD negativity (at cut-offs as described in Section 10.2.7) for ≥ 6 months, and ≥ 12 months, will be summarized and presented as for the primary efficacy endpoint.

As well as summarizing this statistic for the FAS, it will also be summarized similarly for those subjects reaching CR at any time point during treatment.

10.3 Other efficacy analyses

Additional efficacy analyses will include the following. They will be evaluated descriptively and exploratively:

10.3.1 Disease control rate

The disease control rate, defined as the proportion of subjects with a best overall response as CR, PR or SD. The disease control rate will be reported jointly, and using the same methodology, as for the ORR, using both the Lugano and iwCLL criteria.

10.3.2 Measurable and Non-Measurable Lesions

All measurable and non-measurable lesion results will be listed.

The sum of the products of the perpendicular diameters (SPD) for measurable lesions will be included in listings, as well as summarized by visit and best (greatest) reduction per subject. SPD will also be summarized by ADA subgroup, as described in Section 11.8.

Changes in SPD for measurable lesions will also be presented graphically as follows:

- Mean + SE plots over time for actual values
- Mean + SE plots over time for percent change from baseline
- Waterfall plot of best (greatest) reduction per subject
- Individual profile plots of the cross-products of the measurements of each lesion, over time

11 Safety

The primary endpoints for the Dose Escalation part include the number of DLTs during the DLT observation period, the frequency and severity of AEs and SAEs, changes from baseline in laboratory results, and changes from baseline in vital signs. The frequency and severity of AEs and SAEs and the changes from baseline in laboratory results and vital signs are secondary endpoints for the Dose Expansion part.

